4.6 Management of the Non-Eligible Eye

895 In general, non-eligible eyes are treated the same as eligible eyes. The non-eligible eye will have
 896 the same evaluations as the eligible eye. The only difference between eligible and non-eligible
 897 eyes is only the eyes that qualify at baseline (i.e., eligible eyes) will be included in the primary
 898 outcome analysis.

899 If a non-eligible eye worsens, the protocol for worsening of an eligible eye will be used. In the
 900 case of medical therapy, the dosage protocols for acetazolamide and if needed furosemide will be
 901 used. If there is worsening of a non-eligible eye in the optic nerve sheath fenestration group, the
 902 procedure will be performed on the 2nd eye if PMD worsens to -6 dB or worse with size V
 903 perimetry at any time during study follow-up or if the non-eligible eye meets criteria for
 904 temporary treatment failure (see section 5.6.3 below). If there is worsening of a non-eligible eye
 905 in the CSF shunting arm, medical therapy will be given and an evaluation for shunt failure will
 906 be done. Non-eligible eyes can be used to classify the subject as a treatment failure.

907 If only one eye meets study entry criteria and the other eye has worse vision by PMD than the
 908 eligible eye (e.g. PMD worse than -27 dB, refractive error too great, previous damage to the eye
 909 due to trauma, inflammation or infection) treatment of the eligible eye will take precedence; so in
 910 the case of optic nerve sheath fenestration, the eligible eye will be done first. However, there
 911 may be situations where the non-eligible eye requires the first operation. For example, if fixation
 912 is threatened only in the non-eligible eye. If the Site Investigator has concerns about the non-

913 eligible eye and believes it should be operated first, a decision will be made with the Study co-
914 Director as to which eye is operated first.

915 **4.7 Treatment during the Treatment Failure Identification Phase**

916 After the 26 Week primary outcome visit, subjects will transition to the Treatment Failure
917 Identification Phase. Ongoing treatment will continue following the guidelines for the first six
918 months (26 weeks) as long as treatment failure criteria are not met at which time treatment will
919 be at the discretion of the Site Investigator. Investigators are urged to employ treatments from
920 another arm of the study before other treatments under these circumstances.

- 921 **Chapter 5: Study Visits and Procedures**
- 922 **5.1 Randomized Trial**
- 923 **5.1.1 Study Visits and Phone Contacts**
- 924 During the randomized trial, follow-up visits for all three groups will occur at weeks 4, 8 16, and
925 26 (± 7 days) timed from the day of randomization.
- 926 Post-operative visits may also be performed by the surgeon according to the surgeon's usual
927 routine.
- 928 Additional office visits may occur as needed.
- 929 Phone contacts will occur at 12 and 20 weeks (± 7 days).
- 930 **5.1.2 Safety Visits**
- 931 Safety visits will occur in addition to study visits, with the timing dependent on the treatment
932 group. The medical therapy only group generally will have visits 7 days and 14 days (± 4 days)
933 following randomization whereas the surgery groups generally will have visits 7 days and 14
934 days (± 4 days) following each surgical procedure. Visit schedules can be modified at
935 investigator discretion based on the participant's course and the 14-day visit could be skipped if
936 there is substantial improvement in papilledema after 7 days. Additional visits can be scheduled
937 as indicated. Reoperations at any time also will have a similar safety visit schedule.
- 938 **5.1.3 Study Visit Procedures**
- 939 The following procedures will be performed for all subjects at each study visit, unless otherwise
940 specified:
- 941 • Medical/IIH history update
 - 942 • Adverse Events
 - 943 • Concomitant Medications
 - 944 • Vital signs, including weight; (waist circumference at 26 Week only)
 - 945 • Clinical Laboratories
 - 946 • Refraction
 - 947 • Visual Acuity
 - 948 • Ocular Examination
 - 949 • Metabolic Panel (16 and 26 Week only)
 - 950 • CBC (16 and 26 Week only)
 - 951 • Humphrey visual field testing with 24-2 full-threshold program using size V stimulus
 - 952 ➤ at 26 Week, two visual field examinations

953 ➤ At other study visits, one visual field examination will be done, but the VFRC may
954 request the visual field examination be repeated

- 955 • Fundus Photographs
- 956 • OCT* (optic nerve head and macula)
- 957 • Dispense/prescribe acetazolamide and, if needed, furosemide
- 958 • Drug Compliance/Accountability
- 959 • Dietary counseling
- 960 • QoL questionnaires (26 Week only) – at study site or online
- 961 • HIT-6 questionnaire (26 Week only) – at study site or online
- 962 • Lumbar puncture for CSF opening pressure measurement (26 Week; voluntary)

963 *The 26 Week OCT must be done *before* the lumbar puncture.

964 **5.1.4 Phone Contact Procedures**

965 The Site Coordinator will contact the subject by telephone to review adverse events.

- 966 • Medical/IIH History update
- 967 • Adverse Events
- 968 • Review of Concomitant Medications
- 969 • Review of Drug Compliance

970 Additional phone contacts, texts, and emails may be performed as needed.

971 **5.1.5 Safety Visit Procedures**

972 The following procedures will be performed for all subjects at each safety visit:

- 973 • Adverse Events
- 974 • Concomitant Medications
- 975 • Vital signs, including weight
- 976 • Refraction
- 977 • Visual Acuity
- 978 • Ocular Examination
- 979 • Humphrey Visual Field testing with 24-2 full-threshold program using size V stimulus
- 980 • OCT (optic nerve head and macula)
- 981 • Fundus Photographs (only at week 2)
- 982 • Drug Compliance/Accountability

983 **5.2 Treatment Failure Identification Phase**

984 **5.2.1 Follow-up Visits**

985 Follow-up visits will occur at weeks 52 (12 months), 104 (2 years), and 156 (3 years) +4 weeks
986 as long as the study is ongoing.

987 **5.2.2 Study Visit Procedures**

988 Procedures at these visits will include the following:

- 989 • Medical/IIH history update (includes all new treatments and adjustments of dosages)
- 990 • Adverse Events
- 991 • Concomitant Medications
- 992 • Vital signs, including weight
- 993 • Refraction
- 994 • Visual Acuity
- 995 • Ocular Examination
- 996 • Humphrey Visual Field testing with 24-2 full-threshold program using size V stimulus
- 997 • Fundus Photographs
- 998 • OCT (optic nerve head and macula)
- 999 • Drug Compliance
- 1000 • QoL questionnaires – at study site or online
- 1001 • HIT-6 questionnaire – at study site or online

1002 If subject wants to discontinue birth control after the 6-month RCT, this should be discussed with
1003 the Site Investigator.

1004 **5.2.3 Phone Contact Procedures**

1005 A phone, text or email contact will occur at 39 weeks by site staff. Subsequent contacts (every 3
1006 months, starting at month 15 through month 33) will be by Coordinating Center staff for a
1007 structured interview to determine if IIH symptoms have worsened. If the caller has concerns
1008 about the subject, the site investigator will be notified and will be responsible for contacting the
1009 subject.

1010 **5.3 Unscheduled Visits**

1011 An unscheduled visit can be performed at any time at investigator discretion, including the
1012 circumstance where the subject reports that IIH symptoms have worsened or if any unexpected
1013 adverse events develop. Testing performed and management decisions will be dependent on the
1014 circumstances of the visit and the findings.

1015 **5.4 Extra Assessments for Subjects Who Appear to be Worsening**

1016 If a subject appears to be worsening, the subject will receive a combination of frequent contact
 1017 (phone, text, email) and unscheduled visits. The Site Investigator will determine at the end of
 1018 each visit whether the subject appears to be worsening clinically [guidelines being: 1) subject
 1019 report of progressive visual loss, 2) papilledema is worsening, 3) OCT measures are worsening,
 1020 4) ETDRS acuity worsens more than 4 letters, or 5) PMD worsens more than 2 dB]. If the Site
 1021 Investigator is unsure how to proceed, he/she will review the case with the Study co-Director.

1022 **5.5 Early Termination**

1023 For subjects who are withdrawing or being withdrawn from the study, a final visit should be
 1024 scheduled as soon as possible.

1025 Procedures to be performed during the visit are the same as those listed in section 5.1.3.

1026 **5.6 Surgical Malfunction**

1027 VPS and ONSF malfunction will be evaluated at every visit if symptoms and findings suggest it.
 1028 If the Site Investigator, based on all clinical findings, believes that there may be a surgical
 1029 procedure malfunction/failure, he/she will request an SMRC review. Similarly, if the Photo
 1030 Reading Center or Visual Field Reading Center identify lack of improvement or worsening, a
 1031 SMRC review can be triggered.

1032 **5.6.1 Criteria for SMRC Review**

1033 Any of the below can trigger an SMRC review:

- 1034 1. Either visual criteria for treatment failure are met (see section 5.7.1)
- 1035 2. Papilledema: failure of papilledema to improve from baseline or worsening of
 1036 papilledema following improvement
- 1037 3. Site investigator believes there is substantial worsening of the subject's condition even if
 1038 none of the other criteria are met

1039 **5.6.2 Surgical Malfunction Review by SMRC**

1040 When triggered, the SMRC will review all available clinically-related information and reading
 1041 center results to determine whether there is a non-disease associated cause (mechanical cause)
 1042 for the lack of improvement or worsening. The site surgeon and investigator will participate in
 1043 the review process as needed. The SMRC may request that certain exams be repeated for further
 1044 evaluation. The evaluation for VPS may include a radionuclide shunt study. The evaluation for
 1045 ONSF may consider orbital MRI or echography. If the SMRC believes a surgical malfunction is
 1046 likely, the subject's surgical procedure will be evaluated to check the viability of the procedure.
 1047 If the SMRC decides there was a problem with the surgery or a surgical device malfunction, they
 1048 will discuss the case with the site investigator, the surgeon, and the Study co-Director (or
 1049 committee member) to determine whether re-operation is indicated.

1050 The subject's safety is priority so if a site investigator or the SMRC Chair is confident a surgical
1051 malfunction occurred and emergent re-operation is needed, re-operation may be performed prior
1052 to full SMRC review.

1053 **5.6.3 Temporary Treatment Failure**

1054 Temporary treatment failure is a situation that can occur in either of the surgical arms where the
1055 subject meets criteria for treatment failure (see section 5.7.1) and then has their surgical
1056 procedure revised or, in the case of ONSF, either revised or the other eye operated on. If the
1057 subject then recovers vision and no longer meets the criteria for treatment failure, they will
1058 continue the protocol treatment. If repeat surgery is not successful in improving vision out of the
1059 treatment failure criteria range, the case goes to the Adjudication Committee to determine if
1060 treatment failure has occurred.

1061 **5.7 Treatment Failure**

1062 Possible treatment failure will be evaluated at every visit if symptoms and findings suggest it. If
1063 the Site Investigator, based on all clinical findings, believes that there may be a treatment failure,
1064 the worsening will be confirmed with a repeat visual field examination (and ETDRS acuity
1065 testing if needed) on the same day or within four days of the original visual field. If the Visual
1066 Field Reading Center identifies lack of improvement or worsening, the site will be notified and
1067 repeat testing performed. If the worsening is confirmed (both visual field examinations having
1068 PMD that exceeds the cutoff value in 5.7.1 below), the case goes to the Adjudication Committee
1069 to determine if treatment failure has occurred.

1070 **5.7.1 Treatment Failure Criteria**

1071 If either of the below criteria for worsening are met, the subject will be considered for treatment
1072 failure by the Adjudication Committee:

- 1073 1. Worsening of Full Threshold Size V 24-2 Perimetry.
- 1074 a. Average baseline MD is equal to or better than -4 dB and visual function worsens
1075 more than 2 dB MD from the baseline average.
- 1076 b. Average baseline MD is worse than -4 dB and equal to or better than -6 dB and
1077 visual function worsens more than 3 dB MD from baseline average.
- 1078 c. Average baseline MD is worse than -6 dB and visual function worsens more than
1079 4 dB MD from baseline average.
- 1080 2. Worsening of 2 or more lines of ETDRS visual acuity

1081 **5.7.2 Treatment Failure Review by Adjudication Committee**

1082 The Adjudication Committee will review possible treatment failures and determine if a treatment
1083 failure has occurred. The committee will be masked to treatment assignment and using all
1084 available clinically-related information, including fundus photo results, will decide whether the
1085 failure is most likely due to increased intracranial pressure or from another cause, such as
1086 perimetric artifact, poor subject effort, or the presence of another unrelated cause of visual loss.

1087 If the Adjudication Committee determines that a possible treatment failure is most likely due to
1088 IIH, the subject will be classified as having experienced a treatment failure. All cases that are
1089 sent to the Adjudication Committee will be reviewed first by the Study Director. If it is obvious
1090 that the patient meets criteria for treatment failure, they will be so designated. The case will
1091 subsequently be reviewed by the Adjudication Committee.

1092 When a subject meets the criteria for treatment failure, it is preferred that subsequent therapy
1093 come from one of the other two treatment arms but this decision will be deferred to the judgment
1094 of the Site Investigator. These subjects will continue to be followed at their set times for the full
1095 follow-up period (up to 3 years). The date of a confirmed treatment failure will be the date of the
1096 first visual field that triggered the Adjudication Committee review.

1097 If treatment failure is not confirmed, the subject will continue to follow his/her treatment group's
1098 protocol.

1099

[figure not shown]
1100

Figure 3. Algorithm for Review by Surgical Malfunction Review Committee

Criteria for Surgical Malfunction (Temporary TF):

- 1) *Papilledema*: at week 2 or after - failure to improve from baseline or worsening following improvement
- 2) *MD* or *ETDRS* acuity worsening to TF levels
- 3) *Site investigator* worried there is a surgical malfunction

SMRC reviews perimetry, OCT, disc photos, and clinical profile

1101

1102

1103

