 281 lowered post-operatively, but the duration of this effect is unknown. In a meta-analysis of large
 282 case series of ONSF for IIH (Table 2), post-operative visual acuity or visual field results were
 283 equal to, or better than, pre-operative vision in 87% of patients reported. However, 13% of
 284 patients had worse vision in the post-operative period. Up to 50% of patients have post-operative
 285 headache relief with ONSF.⁵ A report on 75 eyes of 54 patients undergoing ONSF suggested that
 286 patients undergoing ONSF may have substantial long-term failure rates.¹²

287 **Table 2. Case series of visual outcome after ONSF.**

Study	Vision Worse	Vision Not Worse	Total
Hupp ⁴⁷	6	11	17
Sergott ⁴⁸	0	23	23
Brouman ⁴⁹	0	10	10
Goh ⁵⁰	9	31	40
Corbett ⁵	1	21	22
Plotnik ⁵¹	4	27	31
Acheson ⁵²	3	17	20
Kelman ⁵³	3	26	29
Banta ⁵⁴	11	75	86
Yazici ⁷	1	16	17
Alsuhaibani ⁵⁵	2	59	61
Pineles ⁵⁶	12	38	50
Fonseca ⁵⁷	3	11	14
Total:	13%	87%	420

288

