1564 concern include the following: death, absence of light perception, hypokalemia (from Lasix use),
1565 surgery-associated visual loss (from either VPS or ONSF), fenestration failure and orbital
1566 infection (from ONSF), and shunt failure, infection, seizures, and subdural hematoma (from
1567 VPS). If potential safety concerns are identified, the DSMC may require review of visual field
1568 data in order to evaluate the risk-benefit of continuing the trial as planned or modifying (or
1569 halting) the trial.

1570 **9.8.2 Interim Analyses for Efficacy**

1571 We propose to perform a single interim analysis for efficacy based on the primary outcome
 1572 efficacy variable. This will be performed after 50% of the subjects have completed (or were
 1573 scheduled to have completed, based on their randomization date) their Month 6 visit and will
 1574 only include data from these 50% of subjects. Given that recruitment of the 180 subjects will
 1575 take place over 3 years, assuming that recruitment is uniform over time, it is anticipated that
 1576 slightly fewer than 70% of the subjects will be enrolled at the time of the interim analysis.

1577 The analysis will involve pair-wise comparisons among the treatment groups with respect to the
 1578 primary outcome efficacy variable; the significance level used for each comparison will be that
 1579 determined by an O'Brien-Fleming α -spending function for a two-group comparison divided by
 1580 3 (Bonferroni correction).⁹⁹ In this case, the boundaries will be $Z = 3.394$ for the interim analysis
 1581 and $Z = 2.400$ for the final analysis. Assuming that there are 30 subjects per group and that the
 1582 standard deviation is 6.5 dB at the interim analysis, the boundary will be crossed if a group
 1583 difference exceeds approximately 5.7 dB. This monitoring procedure will have a negligible
 1584 impact on the overall Type I error probability: the significance level at the final analysis
 1585 corresponding to $Z = 2.400$ is $\alpha = 0.0164$. Point and interval estimates of treatment effects, as
 1586 well as reported p-values, will be adjusted for the interim analysis. The bias-adjusted mean will
 1587 be used for point estimation and confidence intervals and p-values based on the MLE (sample
 1588 mean) ordering of the sample space defined by the group sequential design^{97,98} will be reported
 1589 in this case.

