1749 Each site will be given an internal address and password that allows the site to upload subject
1750 images.

1751 Data will be stored on a secure server. Daily, weekly and monthly backups of the data will be
1752 made with offsite storage as well. Quality Control reports will be prepared on a quarterly basis.

1753 **10.5.4 Optical Coherence Tomography Reading Center (OCTRC)**

1754 The OCTRC will provide training and certification of all technicians (at least 1 per clinic site) so
1755 that valid OCT images are transmitted, read, stored and archived. They will also provide ongoing
1756 assessment of thickness measurements and evaluation of the optic nerve head neural canal shape
1757 deformations to the sites, Jaeb Center, RC, Adjudication Committee, Surgical Malfunction
1758 Review Committee and SSC.

1759 Raw data will be transferred to the OCTRC from the site via UC Davis OCTRC's secure File
1760 Transfer Protocol (FTP) site. These raw data will be uploaded into the Cirrus Research Browser
1761 for assessment and quality control by the OCTRC.

1762 Data will be stored on a secure server. Daily, weekly and monthly backups of the data will be
1763 made with offsite storage as well. Quality control reports will be produced by the OCTRC on a
1764 quarterly basis.

1765 **10.5.5 Surgical Quality Assurance Committee (SQAC)**

1766 There will be a SQAC composed of two orbital surgeons and two neurosurgeons. They will
1767 certify study surgeons and provide quality control, as detailed in the MOP.

1768 **10.5.6 Surgical Malfunction Review Committee (SMRC)**

1769 The SMRC will review patients in the trial that are worsening and determine if possible surgical
1770 malfunction exists. The review is triggered if the criteria described in section 5.6.1 above are
1771 met.

1772 **10.5.7 Adjudication Committee (AC)**

1773 A three member committee appointed by the Study Steering Committee (SSC), plus the Study
1774 Director, will review subjects that meet the criteria for possible treatment failure. All treatment
1775 failure cases will be reviewed first by the Study Director or committee chair for safety reasons.
1776 This committee will be charged with deciding whether the worsening of the subject is most
1777 likely due to increased intracranial pressure and is a failure of therapy, or the worsening of PMD
1778 is more likely due to another reason. A report of all decisions will be sent to the Data and Safety

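### Confirmed visual loss counts as treatment failure if attributed to raised intracranial pressure or IIH; the plan does not say how loss caused by the study operation is classified, so time to failure can favour each surgical arm over medical therapy

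*Protocol*

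**What the plan says.** Protocol 5.7.1 sets visual field and acuity thresholds that send a case to the Adjudication Committee. They do not by themselves make it a failure.

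Under 5.7.2 the committee, masked to treatment, decides whether the "failure is most likely due to increased intracranial pressure or from another cause, such as" "perimetric artifact, poor subject effort, or the presence of another unrelated cause of visual loss". If the loss is judged most likely due to "IIH, the subject will be classified as having experienced a treatment failure". Otherwise: "If treatment failure is not confirmed, the subject will continue to follow his/her" group's protocol. The Study Director sees each case first, and where it is obvious "that the patient meets criteria for treatment failure, they will be so designated. The case will" then go to the committee.

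Section 10.5.7 states the same charge: whether the worsening is most "likely due to increased intracranial pressure and is a failure of therapy, or the worsening of PMD" has some other explanation.

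Protocol 9.8.1 lists among its events of particular concern "surgery-associated visual loss (from either VPS or ONSF), fenestration failure and orbital" infection. Section 1.3.2.2 reports that, in the ONSF case series, 13% of "patients had worse vision in the post-operative period".

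Protocol 9.7 and SAP 3.6 analyse time from randomization to treatment failure by Cox model and Kaplan-Meier curves. Subjects without failure are censored at the last contact at which they were known not to have failed.

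**The concern.** Loss caused by the operation is real and treatment-related, but it is not loss from raised pressure. The committee's question has two answers, and only the raised-pressure answer leads to a confirmed failure. Direct surgical injury can occur only in the two surgical arms, apart from medical-arm subjects who cross over. An event definition that leaves it out can therefore remove events from those arms and not from the medical arm.

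What is at stake is the time-to-failure comparison, which Protocol 1.4.2 treats as a very important outcome and which is the only outcome listed in SAP 3.6. A medical-arm subject who worsens past the 5.7.1 threshold because of IIH is an event. A surgical-arm subject who worsens equally because of the operation may never be one.

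**Working it through.** **Reading the sections together**

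1. Protocol 5.7.2 and 10.5.7 give the same two-way test. Neither names procedure-caused loss.
2. Protocol 5.6.2 has the surgical malfunction committee look for a mechanical cause, which it describes as one not associated with the disease. Under 5.6.3, if repeat surgery does not restore vision, the case goes to the Adjudication Committee, whose test is whether the loss is due to IIH. In the protocol's own terms, then, a surgical cause is not the disease.
3. An unconfirmed subject continues on protocol and remains at risk. Neither Protocol 9.7 nor SAP 3.6 has an any-cause event or a competing-event rule.
4. The censoring sensitivity analysis in both documents changes only subjects censored before their scheduled end of follow-up. It does not reach a subject with surgical visual loss who completes follow-up.
5. The surgical-failure outcomes in Protocol 9.4 concern malfunction. SAP 3.8 tabulates malfunctions, complications and reoperations but does not enter them in the failure comparison.

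**What the documents give on size**

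No event count or power is stated for time to failure; the sample size rests on PMD. The nearest figures are these:
- Table 2: 6+0+0+9+1+4+3+3+11+1+2+12+3 = 55 worse of 420 = 13.1%, which reproduces the stated 13%.
- Table 3: the series reporting vision sum to 38 worse of 374 = 10.2%. The stated 8% matches 38/485 = 7.8%, which includes series where vision was not studied.
- Protocol 9.3.1: at most 15% of subjects expected to fail before Month 6.

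Both tables count worsening from any cause and do not use the 5.7.1 criteria. Neither gives a procedural share, so the bias cannot be computed.

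**Illustration (assumed rates, 60 per arm, two-sided 1.7%)**

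Let F be the true any-cause failure proportion in both arms and s the share of surgical-arm failures excluded. Then:
- observed surgical proportion Fs = F(1 − s)
- observed HR = ln(1 − Fs) / ln(1 − F)
- events D = 60(F + Fs)
- δ = √(D/4) × |ln HR|
- chance of nominal significance = Φ(δ − 2.387) + Φ(−δ − 2.387)

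For F = 0.15 and s = 0.25:
- Fs = 0.1125
- HR = ln(0.8875)/ln(0.85) = 0.734
- D = 60 × 0.2625 = 15.75
- δ = 1.984 × 0.309 = 0.61
- chance = 3.9%, against 1.7% with no exclusion

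| F | s | observed HR (true 1.0) | chance of significance |
|---|---|---|---|
| 15% | 10% | 0.892 | 2.0% |
| 15% | 25% | 0.734 | 3.9% |
| 15% | 50% | 0.480 | 15% |
| 30% | 10% | 0.882 | 2.5% |
| 30% | 25% | 0.715 | 7.5% |
| 30% | 50% | 0.456 | 37% |

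The comparison can also change direction. Suppose 15% fail on medical therapy, and in a surgical arm 10% fail from raised pressure and a further 10% lose vision to the procedure. The observed HR is ln(0.90)/ln(0.85) = 0.65. Counting all confirmed loss, it is ln(0.80)/ln(0.85) = 1.37.

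**The case against.** The strongest reply is that the exclusion is inferred. Section 5.7.2 says that loss due to IIH is failure; it does not say that nothing else is. Its examples of other causes end with an unrelated one, and surgical injury is not unrelated. The Study Director may designate obvious cases first, and a masked committee may not recognise a surgical cause. All of this stands, so a reader who infers that the protocol expressly excludes procedure-caused loss goes further than the text. But the reply leaves the classification of a foreseen, arm-specific event to chance, which is itself a reason to settle it.

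Second, surgical problems have their own route in 5.6, and the Figure 3 algorithm was only partly available for this review. Malfunction that raises pressure can still be confirmed as failure if repeat surgery does not restore vision. The point is therefore limited to direct injury, and the 5.6 route still ends at the same causal question.

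Third, the loss is seen elsewhere. An unconfirmed case contributes its Month 6 PMD to the primary analysis, PMD and acuity changes are analysed at Months 12, 24 and 36, and vision loss is a key safety outcome. This stands: a reader might infer that the primary result is biased in the same way, and the documents do not support that. None of it corrects the hazard ratio, however.

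Fourth, a disease-specific event with separate safety reporting is a defensible choice. It is, provided that it is stated and that an any-cause result is shown beside it.

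**Conclusion.** The concern holds as an ambiguity with a predictable direction. On a plain reading of 5.7.2 and 10.5.7, procedure-caused loss is not confirmed as failure, and nothing in Protocol 9.7 or SAP 3.6 compensates. Each surgical arm compared with medical therapy can look better than it should on time to failure. Between ONSF and VPS the effect favours whichever arm loses more vision to surgery, and the documents do not say which.

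The size is unknown. The HR of about 0.73 rests on three assumptions: equal true failure of 15% (the plan's pre-Month-6 ceiling for all subjects, applied here to each arm), a quarter of surgical-arm failures excluded, and proportional hazards. It shows what could happen and is not an estimate. A reader might take Table 2's 13% as the amount hidden in the ONSF arm. It is not, because it mixes all causes and uses other criteria.

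A reader might also conclude that procedure-caused loss should simply be redefined as treatment failure. The documents do not make that a neutral change. Failure status moves the primary PMD time point (9.3.1), puts later treatment at the investigator's discretion (5.7.2) and triggers an extra visit with all Month 6 procedures (5.7.3).

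**What to change.** - Reconcile 5.7.2, 10.5.7 and 9.8.1 so that the protocol states how procedure-caused loss is classified. Leave unchanged the failure definition that drives treatment and the primary PMD time point.
- Have the Adjudication Committee record two answers in order: first whether the worsening is real, then its cause (IIH or raised pressure; study procedure or study drug; artefact or poor effort; unrelated disease).
- Prespecify in SAP 3.6 a supplementary Cox and Kaplan-Meier analysis of time to any confirmed, non-artefactual worsening that meets 5.7.1, whatever its cause. Use the same covariate, 98.3% intervals and event-date rule as the main analysis, and report it beside the main analysis.
- State in the SAP how temporary failures that recover after revision (5.6.3) enter this analysis, since those cases may never reach the committee.

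The cost is one form field and one more analysis, with no added visits or subjects. Surgical-arm results may look less favourable. Recording a procedural cause carries some risk of revealing the arm to the committee, which asking first whether the loss is real limits. The SAP's revision history records no analyses done at version 1.0; the addition should be made before outcome data are viewed.
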